4.1 Study Periods

4.1.1 Molecular Pre-screening:

Prescreening will be performed on tumor samples from the RC/RNU specimens. Potential subjects will give their consent for testing of their tumor tissue, whereafter they can be screened/enrolled based on local genomic sequencing outcome at the sponsor's central laboratory. The timing of pre-screening consent can be prior to, - or after RC/RNU.

4.1.2 Screening and Treatment Period:

After signing the informed consent form for the complete study, the screening period will then take place in the period after surgery until week 13 after surgery. At Day 1, prior to the start of treatment, results from screening visit evaluations should be reviewed to determine whether the subject continues to meet the eligibility requirements. Subsequent visits during the treatment phase will take place at Day 8, Day 15 and Day 21 and subsequently at 3 week intervals. Timing of subsequent visits can be prolonged to max. 9 week intervals if no problems exist during the first 12 weeks of therapy. Dates for subsequent study visits will be determined based on Day 1, the start of treatment, and should occur within 3 days (±) of the scheduled date unless delayed for safety reasons.

Subjects will self-administer study drug using an oral QD regimen in a continuous dosing schedule. Each dose of Pemigatinib should be taken first thing in the morning upon waking or after a 2-hour fast; subjects should then fast for an additional 1 hour after taking study drug. The starting dose is 13.5 mg Pemigatinib. Study treatment will continue until 12 months, or until the evidence of disease relapse or onset of unacceptable toxicity.

If a dose is missed by more than 4 hours, the subject should skip the dose and take the next scheduled dose at the usual time. Any missed doses reported by the subject should be recorded in the subject's source documents.

4.1.3 End of Treatment

When the subject permanently discontinues study drug, the end of treatment (EOT) visit should be conducted. If the EOT visit coincides with a regular study visit, the EOT evaluations will supersede those of that scheduled visit, and the data should be entered in the EOT visit in the eCRF. The subject should be encouraged to return for the follow-up visit.

4.1.4 Safety Follow-up:

The safety follow-up period is the interval between the EOT visit and the scheduled follow-up visit, which should occur 30 to 35 days after the EOT visit (or after the last dose of study drug if the EOT visit was not performed). Adverse events and SAEs must be reported until at least 30 days after the last dose of study drug; or until toxicities resolve, return to baseline, or are deemed irreversible; death; or initiation of a new anticancer treatment, whichever occurs first. Reasonable efforts should be made to have the subject return for the follow-up visit and report any AEs that may occur during this period.

If a subject is scheduled to begin a new anticancer therapy before the end of the 30-day safety follow-up period, the safety follow-up visit should be performed before new anticancer therapy is started. Once new anticancer therapy has been initiated, the subject will move into the survival follow-up period.

4.1.5 Disease Status Follow-up:

Subjects who discontinue study treatment for a reason other than disease relapse or progression will move into the disease status follow-up period and should be assessed every 12 weeks by radiologic

imaging to monitor disease status. Every effort should be made to collect information regarding disease status until:

- The start of new antineoplastic therapy.
- Disease relapse or progression.
- Death.
- The end of the study.

At disease relapse or progression, a biopsy and subsequent genomic sequencing at the sponsors central laboratory is recommended after written informed consent of the patient.

4.1.6 Survival Follow-up:

Once a subject has confirmed disease relapse or progression, or starts a new anticancer therapy, the subject moves into the survival follow-up period and should be contacted by telephone, email, or visit at least every 12 weeks to assess for survival status until death, withdrawal of consent, or the end of the study, whichever occurs first. The investigator or qualified representative can also use continuing subject records to report data on subsequent treatment regimens, and overall survival in the eCRF.

4.1.7 End of Study:

The end of the study may be designated as the timepoint when all subjects have discontinued the study after 2 years of follow-up or when the sponsor terminates the study.

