A radiological assessment of disease status will be performed at screening (after radical surgery). Subsequently, disease status will be assessed according to daily urological practice until the start of new anticancer therapy, disease relapse, death or end of study. Follow-up imaging scans are usually based on the recurrence possibility (timing, probability, site, and potential treatment) and functional aspects. In spite of low level of evidence, a suggested oncologic follow-up schedule includes CT scans every 4 months during the first year and every 6 months until the third year [22]. During the investigators meeting at the occasion of the annual EAU meeting in Barcelona, on March 17th, 2019, the investigators proposed and agreed to use a 12 weeks interval (+/- 1 week) for imaging procedures in this high risk group of patients. Relapse free survival will be assessed starting from date of first dose and then every 12 weeks until disease relapse or death. Final assessment of the 2-year relapse free survival rate will be done at 2 years. Overall survival will be assessed from the first dose until death (every 12 weeks from disease relapse to death or termination of the study). (See Appendix 6)

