7. STATISTICAL CONSIDERATIONS

7.1 Patient Accrual, Study Duration and Calculation of Patient Numbers

The recruitment period will be 2 years and patients will be followed for an additional 2 years or until relapse or progression. 2-Year relapse-free survival (RFS) rate is the primary endpoint. No interim analyses are planned. Patients will be consecutively molecularly screened and enrolled into the study. It is expected that about 35% of the total screened patients will be eligible and will be enrolled in this study to receive Pemigatinib treatment. Treatment will be continued for a maximum period of 12 months or until the evidence of disease relapse or unacceptable toxicity development. The assumption is that treatment with Pemigatinib will result in a significant higher 2-year RFS rate at 2 years of 45% RFS compared to the reported 30% RFS at 2 years in bladder cancer patients [3].

Statistical Power Calculations:

In an exact single-stage phase II design [24] with power: 0.80; one-sided alpha: 0.10; H0: 2-year RFS: 30%; H1: 2-year RFS: 45% and follow-up duration of 2 years, the total number of eligible and treated patients needed to be enrolled is 50. Patients who withdraw from the study before completing the study period of 2 years, cannot be included in the calculation of the 2-year RFS rate. We estimate that ~15% of the patients will be withdrawn. Therefore, we need a total of 56 patients enrolled. Cut-off to reject the alternative hypothesis H1 is a total of 20 or more patients who experience relapse or progression at or before 2 years of study follow up.

A total of 56 patients needed in this phase II trial is corresponding to approximately 150 patients needed for molecular pre-screening. The primary analysis includes the planned analysis of the primary endpoint 2-year RFS rate which will be analyzed at the 2-years follow-up time point. RFS is defined as the time from the date of start of treatment until disease relapse or progression by investigator determination, or death due to any cause, whichever occurs first. See also 4.4.3.

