7.4.2 Relapse Free Survival Analysis and 2 year RFS rate

Relapse free survival is defined as the time from the date of start of study treatment until disease relapse or progression by Investigator determination, or death due to any cause, whichever occurs first. Relapse free survival will be analyzed and graphically presented by the Kaplan-Meier method. The percentage of patients with relapse free survival at 2 years will be calculated with its 95% Confidence Interval.

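### Disease-status follow-up stops when new anticancer therapy starts, although RFS counts relapse or death regardless of therapy, and no rule says how the affected patients are analysed

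*Combined protocol and SAP*

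**What the plan says.** **The endpoint.** Section 7.4.2 runs RFS from the start of treatment "until disease relapse or progression by Investigator determination, or death due to any cause, whichever occurs first". Section 7.1 gives the same definition. Section 4.4.3 adds that a death without earlier documented relapse is an event. None of the three treats new therapy as an event or as a censoring point.

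**The data collection.** Section 4 has disease status assessed "until the start of new anticancer therapy, disease relapse, death or end of study". Section 4.1.5 repeats that stopping point, listing "The start of new antineoplastic therapy" first among the events that end the collection. Section 4.1.6 says that a patient who has a confirmed relapse, "or starts a new anticancer therapy, the subject moves into the survival follow-up period", where contact every 12 weeks by telephone, email or visit establishes survival status. Sections 4.1.4 and 4.4.4 make the same transfer. Appendix 6 marks CT/MRI under disease-status follow-up and not under survival follow-up.

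**The contrary text.** Section 4 also says that RFS is assessed every 12 weeks until relapse or death, with no stop at new therapy. Section 5.4 encourages patients who stop treatment early to attend the remaining visits, and keeps those who stop for unacceptable drug-related adverse events in follow-up for disease status and survival.

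**The analysis.** A censoring rule is written for overall survival only (Section 7.4.3). Section 7.1 leaves withdrawn patients out of the 2-year rate, but a patient in survival follow-up has not withdrawn. Section 7.2 names the intention-to-treat population for the primary analysis.

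**The concern.** The plan stops collecting one component of its primary endpoint, relapse, at a moment the endpoint definition does not recognise, and goes on counting the other, death. A patient who starts another anticancer drug before relapse is documented can afterwards contribute an event only by dying.

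The analyst would then have to choose between exclusion, censoring, counting deaths only, or treating new therapy as an event, and the plan does not choose. If these patients are at higher risk than average, excluding them or counting only their deaths biases the 2-year rate upward, towards declaring the drug active. Higher risk is plausible when therapy starts on suspicion of relapse, because Section 4.4.3 requires radiological or biopsy confirmation and repeat examination of equivocal findings. It is less clear when a patient changes drug after toxicity.

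**Working it through.** **1. Inputs from Section 7.1.** "one-sided alpha: 0.10", power 0.80, "H0: 2-year RFS: 30" per cent, "H1: 2-year RFS: 45" per cent; and "the total number of eligible and treated patients needed to be enrolled is 50".

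**2. The plan's own figure.** With X the number of relapse-free patients, the smallest n for which some r gives P(X ≥ r | 0.30) ≤ 0.10 and P(X ≥ r | 0.45) ≥ 0.80 is n = 50, with r = 20. The exact type I error is 0.0848 and the power 0.8026, so the 50 is reproduced. The rule used below is therefore at least 20 of 50 relapse-free. Section 7.1 words its cut-off in terms of relapses; that is a separate matter.

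**3. Whose status is lost.**

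| Patient | 2-year status |
|---|---|
| Relapse documented before new therapy | Known: event |
| New therapy without documented relapse, dies by 2 years | Known: event, but any earlier relapse date is lost to the Kaplan-Meier curve |
| New therapy without documented relapse, alive at 2 years | Unknown |

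**4. Size without any assumption on prognosis.** Each patient in the last row could be relapse-free or not, which moves the rate by 1/50 = 2 points. Five such patients leave a 10-point range, against a target difference of 45 − 30 = 15 points.

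**5. Size under assumptions.** The documents give no figures for these patients. Let f be the share starting new therapy without documented relapse, q their true 2-year RFS and s the proportion of them alive at 2 years. Assume f = 5–10%, q = 0–20%, s = 40–60%, and hold the true overall rate at the null of 0.30.

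If only their deaths count, the apparent null rate is p = 0.30 − fq + fs, and the type I error is P(X ≥ 20 | n = 50, p):

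| f | q | s | p | Type I error |
|---|---|---|---|---|
| 0.05 | 0.20 | 0.40 | 0.31 | 0.112 |
| 0.05 | 0 | 0.60 | 0.33 | 0.183 |
| 0.10 | 0.20 | 0.40 | 0.32 | 0.145 |
| 0.10 | 0 | 0.60 | 0.36 | 0.325 |

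The range is about 0.11–0.33, against 0.085 by design.

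If they are excluded, p = (0.30 − fq)/(1 − f), which runs from 0.29/0.95 = 0.305 to 0.30/0.90 = 0.333. With 50 patients still analysed, the type I error is 0.099–0.196. If the exclusions come out of the 50 and the cut-off stays at 20, n falls to 45–48 and the error is 0.04–0.09.

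If new therapy counts as an event, p = 0.30 − fq, which is 0.28–0.30. The type I error is 0.045–0.085. Under the alternative, 0.45 − fq = 0.43–0.45 and the power is 0.71–0.80.

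**6. With complete relapse follow-up** the design is unchanged: n = 50, r = 20, type I error 0.085, power 0.80.

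**The case against.** The strongest case against is that few patients can take this route. Section 4.4.1 does not permit other drugs for muscle-invasive bladder cancer during the study. Section 2 describes a population without options for reducing the risk of recurrence. Section 4.4.3 requires suspected relapse to be confirmed, and Section 5.4 keeps patients who stop for toxicity in disease-status follow-up. Nothing in the documents suggests that 5–10% would start new therapy without a documented relapse. The text is also contradictory rather than uniform, since one sentence in Section 4 already carries RFS assessment on to relapse or death.

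Much of this stands. It makes the number uncertain and possibly small, and it makes the point partly one of reconciliation. It does not close the gap. Sections 4.1.4 and 4.4.4 provide for new therapy within 30 days of the last dose, so the situation is foreseen. The follow-up in Section 5.4 is the follow-up that Section 4.1.5 ends at new therapy. No section supplies the missing RFS rule.

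A reader might infer more than the documents support:

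- *That the endpoint becomes unobservable for a selectively high-risk group.* Only the relapse component is lost, and 2-year status is unknown only for those still alive at 2 years. Their higher risk is an inference.
- *That every way of handling them raises the rate.* Counting new therapy as an event leaves it unchanged or lowers it.
- *That the type I error could reach 0.23–0.55.* That requires every one of these poor-prognosis patients to be alive at 2 years and counted as relapse-free, whereas deaths are events.
- *That excluding them takes the error to 0.10–0.20.* That holds only if 50 patients remain after the exclusions. Section 7.1 expects about 15% withdrawals among 56 enrolled, and Section 5.4 does not replace them.

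**Conclusion.** The concern holds in a limited form. The follow-up sections and the RFS definition disagree about whether relapse after new therapy belongs to the endpoint, and the plan does not say how patients without a known status are analysed. That the endpoint is missing for these patients follows from the text alone, at 2 points of uncertainty each.

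The direction of any bias is conditional: upward if they are at higher risk than average and are excluded or have only their deaths counted. The error range calculated for deaths only rests wholly on the assumed share, prognosis and survival, and should be read as an illustration and not as a forecast. The change is still worth making, because relapses that go unrecorded may not be recoverable later.

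**What to change.** 1. Remove the start of new therapy as a stopping point for relapse data in Sections 4, 4.1.4, 4.1.5, 4.1.6 and 4.4.4, and bring Appendix 6 into line. Amending only some of these would create a new contradiction.
2. In survival follow-up, record relapse status and date up to 2 years from available scans and continuing patient records. Section 4.1.6 already lets sites use those records for later treatments and survival. No additional study-mandated imaging is needed.
3. State in Sections 7.1 and 7.4.2 that the primary analysis counts relapse or death regardless of new therapy.
4. Add a sensitivity analysis that counts the start of new therapy as an event.

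**Cost.** Protocol wording and some extra eCRF entries. The sample size and the 20-patient rule do not change if relapse follow-up is complete. The drawback is that relapse timing after new therapy will depend on routine scans. Section 4 describes usual practice as CT every 4 months in the first year and every 6 months until the third, so those dates will be less regular than under the study's 12-week schedule.

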4.2 Pre-Treatment Tests

4.2.1 Informed Consent Forms and Prescreening Molecular Tests

Subjects must have confirmation of an FGF/FGFR alteration to be considered for the study. Therefore, subjects will be asked to sign a pre-screening consent to allow tumor tissue to be sent to the sponsor's central laboratory (Foundation Medicine) for genetic sequencing. The timing of pre-screening consent can be prior to, - or after RC/RNU. The process of genetic sequencing will take approximately 14 days. Once genetic sequencing has confirmed an FGF/FGFR alteration, a valid informed consent for enrollment in the complete study must be obtained from the study subject before conducting any study-specific procedures.

The Investigator must obtain documented consent from each potential participant prior to participating in a clinical trial. Consent must be documented by the participant's dated signature or by the participant's legally acceptable representative's dated signature on a consent form along with the dated signature of the person conducting the consent discussion. A copy of the signed and dated consent forms should be given to the participant after signature.

Similarly at relapse or progression, subjects will be asked to sign a consent to allow a biopsy and subsequent tumor tissue to be sent to the sponsor's central laboratory (Foundation Medicine) for genetic sequencing.

The initial informed consent form, any subsequent revised written informed consent form and any written information provided to the participant must receive the IRB/IEC's approval/favorable opinion in advance of use. The participant or his/her legally acceptable representative should be informed in a timely manner if new information becomes available that may be relevant to the participant's willingness to continue participation in the trial. The communication of this

information will be provided and documented via a revised consent form or addendum to the original consent form that captures the participant's dated signature or by the participant's legally acceptable representative's dated signature. The informed consent will adhere to IRB/IEC requirements, applicable laws and regulations and Sponsor requirements. The informed consent process for each subject must be documented in writing within the subject source documentation.

4.2.2 Inclusion and Exclusion Criteria

All inclusion and exclusion criteria will be reviewed by the investigator or qualified designee to ensure that the participant qualifies for the trial.

4.2.3 Demographic Data and Medical History

Demographic data such as sex and age will be assessed and recorded by the investigator or a qualified designee. A medical history will be obtained by the investigator or qualified designee. Medical history will include all active conditions, and any condition diagnosed within the prior 10 years that are considered to be clinically significant by the Investigator. Details regarding the disease for which the participant has been enrolled in this study will be recorded separately and not listed as medical history.

4.2.4 Prior Medications Review

The investigator or qualified designee will review prior medication use, and record prior medication taken by the participant within 28 days before starting the trial. Treatment for the disease for which the participant has been enrolled in this study will be recorded separately and not listed as a prior medication.

4.2.5 Disease Details and Treatments

The investigator or qualified designee will obtain prior and current details regarding disease status and all prior cancer treatments including systemic treatments, radiation and surgeries.

4.2.6 Unique Screening Number

All consented participants will be given a unique screening number that will be used to identify the participant for all procedures. Each participant will be assigned only one screening number.

4.2.7 Other Pre-treatment Examinations

The investigator or qualified designee will obtain results of molecular pre-screening, physical examination (length, weight, pulse, blood pressure), WHO performance status, New York Heart Association (NYHA) status, ECG, laboratory and radiological tests as described in the flowchart (Appendix 6). A comprehensive eye-examination should be performed by a qualified ophthalmologist at screening, once every 12 weeks (\pm 7 days), at EOT if abnormalities were shown at the previous, latest examination, and as clinically indicated. The eye-examination should include a visual acuity test, slit-lamp examination, and funduscopy with digital imaging. Additional assessments (eg, Orbital CT) should be done if clinically relevant retinal findings are observed on ophthalmologic exams and in participants with reported visual AEs or change in visual acuity, if the events or changes are suspected to be of retinal origin. Every effort should be made to ensure that all subsequent examinations are performed by the same ophthalmologist.

4.2.8 Registration Procedure

If the patient satisfies all selection criteria, registration or enrollment of a patient in the complete study will be done by the investigator or a qualified representative in the eCRF. For registration the following information will be needed:

- Institutions name
- Name of investigator
- Date of informed consent of the complete study

At registration, a number will be allocated to the patient (patient study inclusion number). This number identifies the patient and must be reported on all eCRF's and other relevant documents. This patient sequential identification number identifies the patient for the Sponsor. The local investigator and his personnel maintain a list which identifies the patients' sequential identification number with the patients source data. This list is safeguarded by the local investigator and his personnel.

4.3 Study Treatment

The investigator shall take responsibility for and shall take all steps to maintain appropriate records and ensure appropriate supply, storage, handling, distribution and usage of investigational product in accordance with the protocol and any applicable laws and regulations.

4.3.1 Supply, Packaging, and Labeling

Study drug will be supplied as 2 mg and 4.5 mg tablets. Pemigatinib tablets will be packaged in high-density polyethylene bottles. No preparation is required.

All Incyte investigational product labels will be in the local language and will comply with the legal requirements of each country.

